6.3.2	Efficacy Analysis	10
6.4	SAMPLE SIZE AND POWER	10
7	STUDY INTERVENTION	12
7.1	DESCRIPTION	12
7.1.1	Treatment Compliance and Adherence	12
8	SAFETY MANAGEMENT	13
8.1	CLINICAL ADVERSE EVENTS	13
8.2	ADVERSE EVENT REPORTING	13
9	STUDY ADMINISTRATION	14
9.1	TREATMENT ASSIGNMENT METHODS	14
9.1.1	Randomization	14
9.1.2	Blinding	14
9.1.3	Unblinding	14
9.2	DATA COLLECTION AND MANAGEMENT	14
9.3	CONFIDENTIALITY	14
9.4	REGULATORY AND ETHICAL CONSIDERATIONS	15
9.4.1	Data and Safety Monitoring Plan	15
9.4.2	Risk Assessment	15
9.4.3	Potential Benefits of Trial Participation	15
9.4.4	Risk-Benefit Assessment	15
9.5	RECRUITMENT STRATEGY	15
9.6	INFORMED CONSENT/ASSENT AND HIPAA AUTHORIZATION	16
9.6.1	Focus Group	16
9.6.2	Intervention	16
9.7	PAYMENT TO SUBJECTS/FAMILIES	16
9.7.1	Payments to subject for time, effort and inconvenience (i.e. compensation)	16
10	PUBLICATION	15
11	REFERENCES	17

ABBREVIATIONS AND DEFINITIONS OF TERMS

CHOP	Children’s Hospital of Philadelphia
T1DM	Type 1 diabetes mellitus
HbA1c	Hemoglobin A1c
SCI	Self-Care Inventory

ABSTRACT

Context:

Type 1 diabetes mellitus is one of the most common chronic diseases in childhood in the United States and its incidence continues to rise. Glycemic control during adolescence can be extremely difficult to achieve due to various biological, social, behavioral, and psychological factors. Development of effective and sustainable interventions to improve diabetes control and diabetes self-management during adolescence is of utmost importance to prevent short- and long-term complications and improve the quality of life of adolescents with type 1 diabetes mellitus.

Objectives:

The primary objective of this study is to test a text messaging intervention using MyDiaText and to determine whether such an intervention will decrease HbA1c in children 12 to 18 years with type I diabetes mellitus.

The secondary objectives is to determine if a text messaging intervention using MyDiaText will improve diabetes self-management skills as measured by the Self-Care Inventory (SCI) in children 12 to 18 years.

Study Design:

Randomized trial

Setting/Subjects:

This study will take place at the Children's Hospital of Philadelphia.

It will include 200 adolescents aged 12-18 with T1DM.

Study Interventions and Measures:

This study will use MyDiaText text messaging program as an intervention.

The main outcome measure will be change HbA1c. The secondary outcome measure will be change in scores of the Self-Care Inventory questionnaire.

PROTOCOL SYNOPSIS

[figure not shown]
Study Title	MyDiaText: Texting the Way to Better Diabetes Control
Funder	NIH T32 Grant-Pediatric Endocrinology Division of CHOP
Clinical Phase	intervention
Study Rationale	Optimal control of type 1 diabetes may prevent, or at least decrease the risk of, diabetes complications. Adolescents with diabetes often have difficulty adhering to a diabetes management plan such a monitoring of blood glucose levels, administering insulin, and eating healthy. There is a need for an intervention that will resonate with youth and support adolescents with type 1 diabetes to improve their self-management practices in order to improve their glycemic control and prevent or reduce the risk of short- and long-term complications.
Study Objective(s)	
Primary
 
 To develop a text messaging intervention using MyDiaText and to determine whether such an intervention will decrease HbA1c in children 12 to 18 years 
Secondary
 
 To determine if a text messaging intervention using MyDiaText will improve diabetes self-management skills as measured by the Self-Care Inventory (SCI) in children 12 to 18 years
Test Article(s)	The intervention will consist of daily text messages sent to the subject's personal mobile device. Previously developed text messages and quiz questions based on the ADA behavior goals will be used for this intervention.
Study Design	Randomized trial
Subject Population key criteria for Inclusion and Exclusion:	
Inclusion Criteria
 
 Subjects age 12 to 18 year of age. Have a diagnosis of T1DM for more than 1 year. HbA1c \geq 8% but $<$ 14%. Have been seen in the diabetes clinic in the last 6 months. Own a personal mobile device with unlimited text messaging plan. Parental/guardian permission (informed consent) and, if appropriate, child assent. 
Exclusion Criteria
 
 Non-English speaking. Significant cognitive disability or major organ illness. Hemolytic anemia.

4. Ongoing oral steroid use	
Number Of Subjects	200 subjects will be recruited from Diabetes Clinics affiliated with the Children’s Hospital of Philadelphia
Study Duration	Each subject’s participation will last for approximately 180 days
Study Phases	(1) Pre-screening : focus groups to determine details of the intervention
Screening	(2) Screening : screening for eligibility and obtaining consent, review medical record for HbA1C, obtain baseline Self-Care Inventory score
Study Treatment	(3) Intervention : review medical record for HbA1C, obtain Self-Care Inventory score
Follow-Up	(4) Follow-up : review medical record for HbA1C, obtain Self-Care Inventory score, complete satisfaction survey
Efficacy Evaluations	The primary efficacy endpoint will have two parts: the change in HbA1c between control and intervention groups between visit 1, 2 and 3.
Safety Evaluations	Adverse events are not anticipated in this study.
Statistical And Analytic Plan	Descriptive data analysis will include estimating means and standard deviations for continuous variables and counts and proportions of categorical variables for all aims. Two sample t-tests will be used to evaluate changes in HbA1c and SCI scores between the control and intervention groups and paired t-tests (or nonparametric methods if data is not normally distributed) will be used to compares the above changes within each group.
Data and Safety Monitoring Plan	The PI will monitor study progress, ensure the accuracy and security of the data, and ensure subject safety.

TABLE 1: SCHEDULE OF STUDY PROCEDURES

Study Phase	Screening	Control	Intervention	Follow-Up
Visit Number		1	2	3
Study Days		90 (+/- 30 days)	90 (+/- 30 days)	1
Informed Consent/Assent	X			
Review Inclusion/Exclusion Criteria	X			
Randomization	X			
Intake Questionnaire		X		
Height and Weight		X	X	X
HbA1c		X	X	X
SCI Questionnaire		X	X	X
Exit Questionnaire (Subjective Assessment of Intervention)				X

FIGURE 1: STUDY DIAGRAM

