3.5 Study Population

3.5.1 Inclusion Criteria

- 1) Males or females age 12 to 18 years.
- 2) Have a diagnosis of T1DM for more than 1 year.
- 3) HbA1c \geq 8% but $<$ 14%.
- 4) Have been in seen in the diabetes clinic in the last 6 months.
- 5) Own a personal mobile device with unlimited text messaging plan.
- 6) Parental/guardian permission (informed consent) and, if appropriate, child assent.

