6.3.2 Efficacy Analysis

The primary analysis will include all subjects randomized at Visit 1 who have gotten HbA1c measurements at visit 2. The primary efficacy endpoint will be the change in SCI Score.

The first analysis will be change in SCI score from visit 1 to visit 2 comparing treatment and control groups. For this analysis we will use paired t-tests to test the null hypothesis of no difference in change in SCI scores at the two-sided $\alpha = 0.05$ level.

The secondary analysis will be the change in HbA1c between the intervention and control group from visit 1 to visit 2. For this analysis we will use two sample t-test to test the null hypothesis of no difference in the change in HbA1c at the two-sided $\alpha = 0.05$ level.

An additional secondary analysis will be the durability of the text messaging intervention from visit 2 to 3. SCI score and HbA1C will continue to be tracked to compare visit 1 to visit 3 and visit 2 to visit 3 at study conclusions.

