6.4 Sample Size and Power

The average HbA1c in adolescents at the CHOP Endocrinology and Diabetes clinic is 9.11% with a SD of 2.26%. Given this average HbA1c and its SD, a sample size of 164 subjects would be needed to observe a difference of 1% in mean HbA1c between groups at a

0.05 level of significance with 80% power in a cross-over study. We will aim to recruit up to 200 subjects out of over 1400 adolescents with T1DM seen at the CHOP Diabetes clinics for their routine care on a yearly basis.

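### The synopsis plans paired t-tests of HbA1c change within each arm, which can show a significant fall without any intervention effect and should be descriptive only

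*Combined protocol and SAP*

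**What the plan says.** The Statistical And Analytic Plan row of the Protocol Synopsis names the between-arm tests first: "Two sample t-tests will be used to evaluate changes in HbA1c and SCI scores between the control and intervention groups". The same sentence then adds paired t-tests, or nonparametric methods if the data are not normal, which "will be used to compares the above changes within each group". Nothing calls these within-arm tests descriptive or limits what may be concluded from them.

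Section 6.3.2 (Efficacy Analysis) compares HbA1c change between arms: "For this analysis we will use two sample t-test to test the null hypothesis of no difference in the change in HbA1c". It neither repeats nor withdraws the within-arm HbA1c tests.

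Section 3.5.1 (Inclusion Criteria) restricts entry to HbA1c of at least 8% and below 14%. Section 6.4 (Sample Size and Power) describes the source population: "The average HbA1c in adolescents at the CHOP Endocrinology and Diabetes clinic is 9.11% with a SD of 2.26" (in per cent). The documents do not discuss regression to the mean, give no visit-to-visit correlation, and do not say which HbA1c measurement decides eligibility.

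**The concern.** A paired t-test within one arm tests whether the mean change is zero. That is the right no-effect hypothesis only if HbA1c would stay level without the intervention. Here subjects are admitted because their HbA1c is high relative to the clinic. When the admitting value also serves as baseline, the next value is expected to lie closer to the clinic mean whatever the subject receives.

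The risk is in the reading. Lowering HbA1c is the primary objective in section 2.1, although section 6.1 makes SCI the primary endpoint. The trial is unblinded (section 3.3). A significant fall with intervention beside a non-significant change in control is easily taken as efficacy, although comparing one arm's p-value with the other's is not a test of the intervention.

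**Working it through.** **The plan's own figure.** Section 6.4 states that "a sample size of 164 subjects would be needed to observe a difference of 1% in mean HbA1c between groups". With SD 2.26, difference 1, two-sided 0.05 and 80% power, the normal approximation gives n per arm = 2 × (1.960 + 0.842)² × 2.26² / 1² = 80.2, so 81 per arm and 162 in total. The t-based version gives 81.15, so 82 per arm and 164 in total. The figure reproduces as a parallel-group size, although section 6.4 calls the design a cross-over. The calculations below use 100 per arm (half of the 200 to be enrolled), with 82 as a check.

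**Inputs from the documents.** Clinic mean 9.11 and SD 2.26 (section 6.4); entry window 8 to below 14 (section 3.5.1); two-sided 0.05 (section 6.3.2).

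**Assumptions.** Visit-to-visit correlation r in the clinic population, varied from 0.6 to 0.9; a normal distribution; qualifying value used as baseline; no drift; no intervention effect. The last four are varied or relied on as stated below.

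**Step 1, the selected group.** The limits are (8 − 9.11)/2.26 = −0.491 and (14 − 9.11)/2.26 = 2.164. The share inside is 0.985 − 0.312 = 0.673. The mean at entry is 9.11 + 2.26 × (0.3536 − 0.0384)/0.673 = 10.17, with SD 1.43.

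**Step 2, expected change with no effect.** Mean change = (1 − r) × (9.11 − 10.17). SD of change = √[(1 − r)² × 1.43² + (1 − r²) × 2.26²].

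**Step 3, chance of a significant fall in one arm.** This comes from the noncentral t with noncentrality √n × mean/SD. The nominal rate in that direction is 2.5%.

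| r | Mean change | SD of change | n = 100 | n = 82 |
|---|---|---|---|---|
| 0.9 | −0.11 | 0.995 | 18% | 16% |
| 0.8 | −0.21 | 1.39 | 33% | 28% |
| 0.7 | −0.32 | 1.67 | 47% | 40% |
| 0.6 | −0.42 | 1.90 | 60% | 52% |

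Simulation (4,000 trials) agrees with the n = 100 column to within about a percentage point.

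**Step 4, the misleading pattern.** In simulation at 100 per arm, a significant fall with intervention and no significant change in control occurs in 14%, 22%, 25% and 24% of trials at r = 0.9, 0.8, 0.7 and 0.6. Without regression to the mean it would be 0.025 × 0.95 = 2.4%.

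**Step 5, relaxing the assumptions (n = 100).**
- *Right-skewed HbA1c* (lognormal above an assumed floor of 5, same mean and SD): mean at entry 9.82; expected fall 0.04, 0.08, 0.14 and 0.20; chance of a significant fall 6%, 9%, 13% and 18% at r = 0.9, 0.8, 0.7 and 0.6.
- *Eligibility on an earlier HbA1c, normal model*: about 2.5% (no inflation) if all visits are equally correlated; 16% to 25% for r = 0.9 to 0.6 if correlation decays with time.
- *Upward drift of 0.2 points, normal model, qualifying value as baseline*: at r = 0.8 the expected change becomes −0.21 + 0.20 = −0.01 and the chance drops from 33% to 3%. At r = 0.9 it is 0.2%, and a significant rise then appears 15% of the time.

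**Step 6, the between-arm test.** In the same simulated trials the two-sample t-test on change rejects 4.6% to 5.3% of the time under the normal, same-value model, and 4.4% to 5.8% over all scenarios run. The expected drop is the same in both randomized arms and cancels.

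**The case against.** A reader might infer that the within-arm null is false by design in both arms, or that a spurious fall will often appear. The documents do not support either as a certainty, because both need the qualifying HbA1c to be the baseline. Some text points that way: section 3.4.1 puts screening on the first day of phase 1, section 4.2 labels the screening visit as visit 1, and Table 1 has no HbA1c in the screening column. Other text points the other way: sections 3.2.1 and 9.5 have clinic schedules checked against the inclusion criteria before subjects are approached, and sections 4.3.1 and 5.3.1 describe an HbA1c measured at visit 1. The distribution shape matters too. A normal model with these parameters puts about 3% of the clinic below an HbA1c of 5%, so the lower, right-skewed figures deserve equal weight. Section 1.3 also cites a study whose historical controls worsened, by an amount not given, and such drift works against regression to the mean. All of this stands.

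A reader might extend the argument to SCI. Nobody is selected on SCI, so regression to the mean is not shown for it. A within-arm SCI test still does not test the intervention, since it has no control comparison.

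A reader might also infer that the HbA1c efficacy result is biased. It is not: the planned comparison in section 6.3.2 is between randomized arms, and step 6 shows that it is sound in this respect. The harm depends on how a supplementary p-value is read.

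What the objection does not rescue is the within-arm test itself. Regression to the mean pushes the no-effect change down and drift can push it up. No text in the plan makes zero the right reference, and nothing labels the result descriptive.

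**Conclusion.** The point holds in a limited form. The within-arm HbA1c tests in the synopsis do not test the intervention, and a significant fall from them can arise without any effect. The 18% to 60% range rests on a normal shape, no drift, the qualifying value as baseline, and r of 0.9 to 0.6; right skew alone lowers it to 6% to 18%. Since the documents settle none of these inputs, no single rate can be given. The change is worth making because the tests add nothing to the randomized comparison and can mislead.

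**What to change.** In the Statistical And Analytic Plan row of the synopsis, replace the within-group paired tests and their nonparametric versions with descriptive within-arm mean change in HbA1c and SCI, with SD or confidence interval and no p-values. State there that efficacy conclusions rest only on the randomized between-arm comparison and that within-arm change does not measure the intervention effect. This costs about two sentences and no data, sample size or power for the between-arm tests.

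One neighbouring text needs its own correction and is not repaired by this edit: section 6.3.2 names a paired test for the treatment-versus-control comparison of SCI ("For this analysis we will use paired t-tests to test the null hypothesis of no difference in change in SCI scores"), whereas the synopsis names a two-sample test.

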1 BACKGROUND INFORMATION AND RATIONALE

1.1 Introduction

Type 1 diabetes mellitus (T1DM) is one of the most common chronic diseases in pediatrics in the United States with more than 18,000 children diagnosed every year. Management of T1DM in adolescence is challenging because pubertal hormonal changes result in insulin resistance and accelerated growth changes insulin requirements. Adolescence is also a time when diabetes care is being transferred from parent to child resulting in more diabetes self-management, which often leads to sporadic blood glucose monitoring and insulin administration resulting in poor diabetes control evidenced by elevated HbA1c. As a result, it is of utmost importance to develop effective interventions for adolescents that optimize their diabetes control. The use of technology has been shown to be a successful intervention in adolescents with chronic diseases and seems to be a promising intervention for adolescents with T1DM as well.

A recent review on the use of technology for adolescents with T1DM showed some improvements in HbA1c as high as a 1% decrease as well as improvement in diabetes self-management. These interventions included text messaging communication, phone and video communication, and smartphone applications. However, most studies have been small, interventions have been cumbersome, and most did not include a diverse sample of adolescents. A larger study using a feasible intervention in a diverse population is necessary to develop and evaluate an intervention that would be effective in improving diabetes control in adolescents.

1.2 Name and Description of Intervention

MyDiaText is an SMS texting program and website mydiatext.com developed by an interdisciplinary team of students, faculty, and clinicians from University of Pennsylvania School of Nursing and School of Engineering and Applied Sciences and the Children's Hospital of Philadelphia that follows the National Standards for Diabetes Self-Management Education established by the American Diabetes Association. It was developed to support behavior change in children aged 10-17 years with T1DM. A feasibility study was done with 20 adolescents (10 of whom identified as non-White) involving daily text messages for a 1 month period. This study showed the use of this application to be feasible and well received in this population.

1.3 Relevant Literature and Data

Each year, more than 18,000 children under the age of 20 are diagnosed with T1DM [1]. Management of T1DM is very demanding as it requires lifelong frequent blood sugar checks, frequent insulin administration, and many lifestyle changes or modifications to maintain good diabetes control. This is particularly challenging in adolescence for a number of reasons. Hormonal changes during puberty can result in insulin resistance necessitating increased insulin doses [2]. Adolescence is also a period of rapid growth which also increases the insulin requirement. Most importantly, parental involvement in the diabetes management generally decreases with increasing age of the child resulting in medical independence. This often occurs prematurely and leads to decreased blood glucose

monitoring and insulin administration, which results in poor diabetes control and can lead to significant morbidity and mortality.

Technology, in particular the use of text messaging, appears to be a good vehicle for interventions in adolescents because of its pervasive use in this population. About 3 in every 4 children aged 12-17 own a cell phone. Studies have shown that 75% of teenagers text, with 63% of them sending text messages on a daily basis [3]. This is also true in low income, urban, and minority adolescents. Some studies have shown high access to technology in this population with estimates of 94% sending text messages on a daily basis [4,5].

Interventions using text messages in adolescents with T1DM have been carried out previously with high levels of satisfaction, but variable improvements in diabetes control measured by HbA1c [6,7]. One intervention involved weekly text messages of encouragement based on self-identified barriers to diabetes self-management [8]. This intervention did not result in a change from baseline HbA1c after 3 months of intervention, but a matched historical control group had significant worsening of glycemic control. Another intervention involved automated text or email messages on blood glucose monitoring sent on a self-selected schedule [9]. This intervention showed a slight but not significant improvement in HbA1c after 3 months. Another intervention involved regular text messages based on diabetes goals compared to the same intervention in addition to an intensive insulin regimen [10]. This intervention lasted 12 months and at its conclusion there was a significant improvement in those adolescents receiving the intervention plus intensive insulin regimen, but no significant improvement in those receiving the intervention alone. All of these studies were rather small, with only 18-33 subjects per group. Of these interventions, only the third study reported race/ethnicity information and only included 4% non-White population.

While studies around text messages have been promising, they have not been conclusive. A systematic review of text messaging studies in T1D concluded that while text message interventions are likely a valuable behavioral change tool, that further research should be grounded in behavioral theory[14]. A study in the adolescent T1D population showed that financial incentives for adherence to blood glucose monitoring showed increased monitoring during the incentive period but not in follow up [15]. A study showing the effect of reward for engagement in diabetes education via text message does not exist.

1.4 Compliance Statement

This study will be conducted in full accordance with all applicable Children's Hospital of Philadelphia Research Policies and Procedures and all applicable Federal and state laws and regulations including 45 CFR 46, 21 CFR Parts 50, 54, 56, 312, 314 and 812. All episodes of noncompliance will be documented.

The investigators will perform the study in accordance with this protocol, will obtain consent and assent, and will report unanticipated problems involving risks to subjects or others in accordance with The Children's Hospital of Philadelphia IRB Policies and Procedures and all federal requirements. Collection, recording, and reporting of data will be

accurate and will ensure the privacy, health, and welfare of research subjects during and after the study.

2 STUDY OBJECTIVES

The purpose of the study is to determine if an intervention using MyDiaText for adolescents with T1DM will improve their glycemic control and self-management skills.

2.1 Primary Objective (or Aim)

The primary objective of this study is to develop a text messaging intervention using MyDiaText and to determine whether such an intervention will decrease HbA1c in children 12 to 18 years. This will be divided into 2 parts:

- To determine whether this intervention will decrease HbA1c in children 12 to 18 years after 3 months +/- 1 month.
- To determine whether the effect of the intervention persists after an additional 3 months +/- 1 month of intervention.

